Aim 3: To compare postoperative rates of surgical site infection (SSI) in women who receive chlorhexidine gluconate versus povidone iodine vaginal antiseptic preparation preoperatively, defined as per CDC guidelines (described below). **Hypothesis:** Chlorhexidine gluconate will demonstrate a non-inferior rate of postoperative SSI compared to povidone iodine.

Aim 4: evaluate vaginal and vulvar irritation for post groups on postop day 1 as measured by a 5-point vaginal irritation scale previously used in a safety and tolerability study examining vaginal chlorhexidine gluconate (Al Niaimi et al) **Hypothesis:** Chlorhexidine gluconate will demonstrate a non-inferior rate of postoperative vaginal and vulvar irritation for postop day 1.

2. Background

Steady improvements have been made in surgical infection control over the past century including improved instrument sterilization methods, operating room ventilation, surgical barriers including gowns and drapes, surgical technique, preoperative antimicrobial prophylaxis, and preoperative cleaning or prepping of the surgical site. Despite these advancements, UTIs and SSIs continue to be a common cause of postoperative morbidity.

Urinary Tract Infections are one of the most common post-operative complications associated with urogynecologic surgery. One study estimated that 33% of women develop UTIs in the 12 week period following surgical treatment for stress urinary incontinence (Anger et al). UTIs are associated with increased health care costs, antibiotic resistance, and morbidity and mortality for patients. Because UTIs are so common, they are used as a quality metric and tracked by the Joint Commission, the Centers for Medicare and Medicaid Services (CMS), and National Surgical Quality Improvement Program (NSQIP), among others.

Another concern following pelvic surgery (which may include a vaginal approach or surgery on the vagina) is development of surgical site infections (SSI). A recent study found that SSIs were among the most common healthcare-associated infection, accounting for 31% of all healthcare-associated infections (HAI) among hospitalized patients. (Magill 1) Vaginal surgery is classified as clean-contaminated procedures because of the natural bacterial flora of the vagina. This generally increases infection risk over clean procedures.

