The primary outcome of this study is to determine rates of urinary tract infections in the period 2 weeks post-surgery for both cohorts. For the purposes of this study, UTI has been defined in section 1 (objectives), aim 1. We have powered the study based on a 10% difference in UTI rates between groups within 2 weeks of surgery. Based on a non-inferiority study design and a between group difference of less than or equal to 10%, we need 58 patients per group (chlorhexidine gluconate versus povidone iodine) to detect no difference with an alpha =0.05 and with 80% power. Assuming a high dropout rate of 20%, we will enroll a total of up to 200 patients (100/group), or until we reach our primary endpoint of 2 week follow up for 116 patients, or 58 patients in each group. We have increased the numbers due to COVID-19 and loss to follow-up.

This is not a multi-center study. Data will be housed at the Eubank clinic.

6. Study Timelines

Timeline	May 2019- April 2020	May 2020-Sept 2020
Subject recruitment, therapy, through 3 month follow up	x	x
Data analysis		x
Manuscript preparation		x

Over the past 12 months, 318 urogynecology cases were performed at UNM and SRMC. Assuming a conservative estimate of 50% enrollment, recruitment of up to 200 patients would be feasible over the next 3 month period.. Since subjects will be followed for 6 weeks after surgery, it may take up to 14 months to collect 6 weeks of follow up data. We estimate that data analysis, manuscript preparation and publication will take an additional 10 months.

7. Study Endpoints

The **primary endpoint** of our study is to determine the incidence of urinary tract infections within weeks of surgery in women who undergo pelvic surgery (which may include a vaginal approach or surgery on the vagina) with either chlorhexidine gluconate or povidone iodine vaginal antiseptic preparation. Our **secondary endpoints** are to investigate SSI rates in the two groups at 6 weeks, and vaginal irritation on the first postoperative day.

Given the extremely low-risk nature of the therapeutic interventions, we do not have any **safety endpoints**. However, any patients noted to have an allergic response will be treated according to the normal standard of care depending on the severity of their allergic reaction.

8. Research Setting

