If a patient demonstrates an allergic reaction to either antiseptic (povidone iodine or chlorhexidine gluconate), they will be routinely treated for allergic symptoms and informed of the antiseptic type, the allergy will also be added to their medical record.

Table 1: Outcomes collected at various time points

	Baseline	2 weeks	6 weeks
Demographic and medical history	X		
Follow up questionnaire	X	X	X
Vaginal irritation questionnaire	Postop day 1		

Our primary outcome is to report the rates of postoperative urinary tract infections for each cohort at 2 weeks postoperatively. It is our standard of care to see patients back at 2 weeks and 6 weeks following surgical management of urogynecological conditions.

If patients are unable to follow up in clinic as standard care, telephone communication may be used to ask patients if they have received care at an outside facility for urinary tract infection or other infection related to surgical treatment.

Outcome Measures:

- Urinary tract infection (UTI): Patients with >100k colony forming units on urine culture, symptomatic patients with >10k colony forming units on urine culture or reported UTI symptoms resulting in empiric treatment without urine culture.**
- Surgical Site Infection (SSI): Surgical site infection as defined by the below criteria in the 6 week postoperative period.**

- 1) We will categorize SSI based on CDC criteria (ref) adapted from the CDC guidelines as referenced below. We will record SSI events 6 weeks after surgery.
 - a. CDC Criterion: Surgical Site Infection (SSI)
 - i. Superficial incisional SSI must meet the following criteria:
 1. Date of event for infection occurs within 6 weeks after any operative procedure (where day 0 is the procedure date)
 2. AND involves only skin and subcutaneous tissue of the incision
 3. AND patient has at least one of the following:
 - a. Purulent drainage from the superficial incision.
 - b. Organisms identified from an aseptically-obtained specimen from the superficial incision or subcutaneous tissue by a culture or non-culture based microbiologic testing method which is performed for purposes of clinical diagnosis or treatment (for example, not Active Surveillance Culture/Testing (ASC/AST).

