 - c. an abscess or other evidence of infection involving the organ/space that is detected on gross anatomical or histopathologic exam, or imaging test evidence suggestive of infection. AND meets at least one criterion for a specific organ/space infection site.

13. Data Analysis

Data Analysis: Between and within group differences will be evaluated using Wilcoxon-Mann-Whitney test for categorical variables and t-tests for continuous variables. If there are any baseline differences between groups, a multivariate analysis will determine the contribution of these differences to observed differences (if any) between groups.

Power Analysis: Power analysis was performed based on previously reported rates of postoperative urinary tract infection after urogynecologic surgery as well as rates of relative reduction in infection with chlorhexidine presurgical preparations as opposed to povidone iodine. To achieve significance for a non-inferiority study using these assumptions we would need 116 patients, 58 per group to detect this difference with $\alpha = 0.05$ and with 80% power.

To allow for a dropout or loss to follow up of 20% due to the pandemic, we will enroll at least 200 patients.

Comparative Cost Analysis

The cost analysis will be conducted from patient and health system perspective and will be expressed as incremental cost required to prevent one episode of UTI.

Direct and indirect cost of health care utilization will be obtained when episodes of UTI occur, including the patient reported travel expenses and copays to obtain care, cost of UTI diagnosis with urine dipstick, urinalysis, and urine culture standardized to University of New Mexico Health Sciences Center institutional pricing as well as the cost of antibiotics for treatment.

14. Provisions to Monitor the Data to Ensure the Safety of Subjects

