The patients who would like to participate in the study will be consented during their new or return visit in the urogynecology clinic or by phone due to the current pandemic. Verbal consent will be noted on the updated consent form with a space to also sign. Due to the pandemic, research coordinators are mainly working from home and going through the consent with participants by phone for the safety of everyone. Privacy is still maintained as the coordinator ensures they have a place they can talk privately by phone. They will have these multiple opportunities to ask any questions that they may have, and they will also be provided with the clinic’s contact information to get in touch with research investigators to address any additional questions or concerns. If they decide to participate at the next visit, they will be allowed to join as long as their surgical procedure has not been completed.

Subjects will be reassured that participation is completely voluntary and does not affect their treatment, their relationship with their providers, or the university to minimize the possibility of coercion or undue influence. The patients will be asked that they understand the opportunity to participate and their complete freedom to decline. This will also be asked if they understand and if they have any questions. There is no minimum time period needed between informing

the patient of the study and time of consent. Subjects will be encouraged to take as much time as they need.

This study will obtain HIPAA authorization prior to enrollment. HIPAA authorization is imbedded within the study consent form, which will be reviewed with all participants by the physician or research staff obtaining consent. Specific information that will be obtained includes prior medical history, surgical history, reproductive health history including child bearing, drug allergies, age, and ethnicity. This information will be obtained by health care providers, not research coordinators, as deemed necessary for a more complete and accurate medical history of the patient.

The HIPAA form is included in the consent attached.

Subjects not fluent in English

Spanish speaking patients will be included in the study, and fully translated consents will be available in Spanish. Consent process for Spanish speaking patients will be conducted through a Spanish interpreter or with a research protocol member fluent in Spanish.

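### Section 13 assigns the independent-samples Wilcoxon-Mann-Whitney test to every categorical variable and to within-group differences, which does not suit unordered variables with three or more levels or repeated categorical items (minor)

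*Combined protocol and SAP*

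**What the plan says.** One sentence in Section 13 (Data Analysis) names the tests: "Between and within group differences will be evaluated using Wilcoxon-Mann-Whitney test for categorical variables and t-tests for continuous variables". It separates variables only into categorical and continuous. It does not distinguish ordered from unordered categories, or independent from paired data. Chi-squared, Fisher's exact, McNemar and signed-rank tests are not named anywhere in the document.

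The next sentence gives the baseline comparisons a role: "If there are any baseline differences between groups, a multivariate analysis will determine the contribution of these differences". No threshold for a difference is stated, and no covariates are listed in advance.

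The variables to which these sentences apply are described elsewhere:

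- Section 25 (Consent Process) lists items to be obtained, including "reproductive health history including child bearing, drug allergies, age, and ethnicity".
- Table 1 in Section 12 marks the "Follow up questionnaire" at baseline, 2 weeks and 6 weeks. The irritation questionnaire is given once, on postoperative day 1.
- Section 5 makes UTI within 2 weeks the primary outcome: "The primary outcome of this study is to determine rates of urinary tract infections in the period 2 weeks post-surgery for both cohorts".
- Aim 4 in Section 1 assesses irritation "as measured by a 5-point vaginal irritation scale".
- All four aims in Section 1 compare the two antiseptic groups with each other.

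**The concern.** Wilcoxon-Mann-Whitney is a two-sample rank test, and the sentence stretches it in two directions.

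**Unordered categories.** With three or more categories and no natural order, the analyst must choose numeric codes before ranks exist, and the p-value depends on that choice. The same imbalance can be missed or found. Because baseline differences lead to a multivariate analysis, an arbitrary coding could decide whether an adjusted comparison is produced. That matters more where the plan leaves the criterion open and the surgeon is not masked (Section 3).

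**Within-group differences.** Answers from the same woman at baseline, 2 weeks and 6 weeks are paired, whereas Wilcoxon-Mann-Whitney treats the time points as separate samples. For categorical items the mismatch is explicit in the text. For continuous items the plan says only that t-tests will be used, so the pairing is unstated.

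**Working it through.** The plan gives no figure for this point, so there is nothing of its own to reproduce. The figure of 58 per arm is the evaluable number in Section 5. The cell counts and correlations below are assumptions chosen for illustration.

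**1. Unordered variable, three levels: 24/10/24 versus 17/24/17.**

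Column totals are 41, 34 and 41, so the expected counts per arm are 20.5, 17 and 20.5. Chi-squared = 4 × 3.5²/20.5 + 2 × 7²/17 = 2.39 + 5.76 = 8.15 on 2 df, p = 0.017. This value does not depend on the codes.

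For Wilcoxon-Mann-Whitney, the expected rank sum in the first arm is 58 × 117/2 = 3393. The tie-corrected variance is (58 × 58/12) × [117 − (2(41³ − 41) + (34³ − 34))/(116 × 115)] = 280.33 × (117 − 13.27) = 29,079, so the SD is 170.5.

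- Second category coded in the middle: midranks are 21, 58.5 and 96. Rank sum = 24 × 21 + 10 × 58.5 + 24 × 96 = 3393. z = 0 and p = 1.00.
- Second category coded lowest: midranks are 17.5 (second), 55 (first) and 96 (third). Rank sum = 10 × 17.5 + 24 × 55 + 24 × 96 = 3799. z = 406/170.5 = 2.38 and p = 0.017.

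Two of the six codings give 1.00 and four give 0.017.

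**2. Other illustrative tables, 58 per arm, over all codings.**

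| Table | Chi-squared p | Wilcoxon-Mann-Whitney p |
|---|---|---|
| 30/10/18 v 18/22/18 | 0.024 | 0.007 or 0.157 |
| 25/15/10/8 v 15/25/8/10 | 0.142 | 0.021 to 0.555 |
| 20/8/20/10 v 10/20/9/19 | 0.0015 | 0.0002 to 0.98 |

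The error runs both ways: some codings hide an imbalance that chi-squared shows, and others suggest one that it does not.

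**3. Binary outcome: 12/58 versus 6/58.**

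Uncorrected chi-squared is 2.367, p = 0.1239. Wilcoxon-Mann-Whitney without continuity correction equals chi-squared × (N − 1)/N = 2.367 × 115/116 = 2.347, p = 0.1255. Swapping the two codes changes nothing.

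**4. Within-group, five-level ordered item, 58 women measured twice.**

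This is a simulation of 2,000 data sets per row, from bivariate normal scores cut into five levels, tested at 5%. Power is for a shift of 0.35 SD on the underlying scale. Each cell gives Wilcoxon-Mann-Whitney, then signed-rank.

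| Assumed correlation | Rejection under no change | Power |
|---|---|---|
| 0 | 4.7% v 5.2% | 43% v 42% |
| 0.3 | 2.3% v 5.6% | 41% v 53% |
| 0.5 | 1.0% v 4.5% | 40% v 65% |
| 0.7 | 0.1% v 5.2% | 38% v 82% |

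Ignoring the pairing gives too few rejections when the correlation is positive, and makes no material difference at zero correlation.

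**The case against.** The strongest case on the other side is that nothing here touches what the trial sets out to show. UTI, and SSI as a rate, are binary, so Wilcoxon-Mann-Whitney is essentially chi-squared and coding is irrelevant. Irritation is ordered, which suits the test, and it is measured once, so it has no within-group change. No aim is a within-group comparison. All of that stands, and it is why the point is minor.

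A reader might also infer more than the documents support:

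- **That the plan uses unpaired t-tests within groups.** It does not say so. A paired t-test is also a t-test, so this is an omission, and power losses calculated for an unpaired t-test would rest on an assumption.
- **That many baseline variables are affected.** Ethnicity is the only documented item that is plausibly unordered with several levels, and its number of levels is not visible. History items may be recorded as yes/no, which are immune. Place of surgery varies (Section 4) but is not listed in Section 12 among the baseline survey items.
- **That coding decides adjustment.** Section 13 states no p-value threshold, so this follows only if the trigger is read as a significance test.
- **That false-positive within-group findings would result.** With positive correlation the test is conservative.

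The example tables can fairly be called extreme: the first is symmetric by construction, and the last shows an imbalance that randomisation would rarely produce. The middle two are milder and still cross 0.05 by coding alone. The contents of the follow-up questionnaire are not shown, so whether it holds any item suited to a baseline-to-follow-up test is unknown.

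**Conclusion.** The sentence is wrong as written, and the consequence is secondary. For unordered variables with three or more levels, the named test gives a p-value that depends on arbitrary codes (0.017 or 1.00 in one illustrative table, 0.007 or 0.157 in another). For repeated categorical items it ignores pairing: at an assumed correlation of 0.5 the rejection rate under no change is about 1% instead of 5%, and power is 40% against 65% for signed-rank.

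The reach is limited to descriptive baseline tables, possibly the decision to run the multivariate analysis, and any within-group comparisons that may be reported. A reading that the primary UTI conclusion is compromised by this choice of test is not supported: the binary comparison is unaffected by coding. Whether either named test addresses the non-inferiority margin is a separate question. The coding dependence itself is certain. Its practical size rests on the assumed tables and correlations, and on how the adjustment trigger is read.

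**What to change.** Replace the test sentence in Section 13 with one that assigns tests by type of variable:

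- unordered and binary baseline variables: chi-squared, or Fisher's exact test where counts are small;
- ordered scales, such as the 5-point irritation scale: Wilcoxon-Mann-Whitney;
- continuous variables between groups: two-sample t-test;
- within-group comparisons: delete them, since no aim uses them, or name paired methods (McNemar for binary items, Wilcoxon signed-rank for ordered items, paired t-test for continuous items).

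This removes the coding dependence but leaves the data-driven trigger for the multivariate analysis in place. If the sentence is being edited anyway, the sponsor should also state what counts as a baseline difference. The cost is one sentence of text, with no change to data, procedures or number of patients.

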This single masked, non-inferiority randomized controlled trial will be conducted at the UNM Eubank Clinic and SRMC Urogynecology clinic and associated operating rooms. We will recruit at least 200 participants between the sites. All collaborating investigators are members of the Urogynecology division at UNM.

The primary aim of our study is to determine if UTI rates are similar between typical preoperative vaginal antiseptic cleaning solutions (i.e. chlorhexidine gluconate vs. povidone iodine). The target population will be patients with urogynecologic conditions desiring surgical management that would require vaginal surgical preparation. If a patient decides during their clinic visit to proceed with surgical management that would require vaginal surgical preparation they will be considered for the study. If the patient is interested in surgical management and fulfills study inclusion criteria, we will then offer her the choice of participating in this study. Written or verbal consent will be obtained from all participants by research staff prior to enrollment. All participants will then complete baseline surveys including patient demographics, medical/surgical history, and contact information, which are attached as supporting documents. This information will be collected from the patient on the day of enrollment with information supplemented from their medical record as needed.

Randomization assignment will be generated by a computer based randomization table and assigned by a research coordinator. Assignments will be kept in sealed opaque envelopes

numbered sequentially. On the day of the patient’s surgery, after previously signing or verbalizing consent and deciding to participate, the next envelope in the sequence will be opened, randomizing the patient to chlorhexidine gluconate or povidone iodine. The therapy allocation will then be carried out.

Patients randomized to chlorhexidine gluconate or povidone iodine will undergo standardized preoperative surgical site preparation by surgical staff. Abdominal cleaning will be done with chlorhexidine gluconate in 70% isopropyl alcohol as this is the standard antiseptic used throughout the institution. Vaginal antiseptic cleaning will be performed with either chlorhexidine or povidone based on the randomization scheme, this will be performed in a standardized fashion as described in supplemental vaginal preparation instruction document (included in appendix A).

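### Covariate adjustment is triggered by observed baseline differences, and the covariates, model, effect scale and deciding analysis stay open until the data are seen

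*Combined protocol and SAP*

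**What the plan says.** Section 13 (Data Analysis) has one sentence on adjustment: "If there are any baseline differences between groups, a multivariate analysis will determine the contribution of these differences". The sentence goes on to relate those baseline differences to whatever outcome differences are observed between the arms. It follows the only statement of the main tests: "Between and within group differences will be evaluated using Wilcoxon-Mann-Whitney test for categorical variables and t-tests for continuous variables". No risk difference or confidence interval is named for the binary UTI outcome.

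The margin is in Section 5 (Number of Subjects): "Based on a non-inferiority study design and a between group difference of less than or equal to 10" per cent. I read this as 10 percentage points absolute, which the text does not say outright.

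Baseline data will be available. Section 12 (Study Procedures) states: "All participants will then complete baseline surveys including patient demographics, medical/surgical history, and contact information". Sections 12 and 16 describe a computer-generated randomisation table in sequential sealed envelopes and name no stratification factors, so the design supplies no default covariates.

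**The concern.** Randomisation makes baseline differences between the arms as allocated a matter of chance. Whether a variable happens to differ and whether it predicts UTI are separate questions, and only the second justifies adjusting for it. A rule driven by observed imbalance can therefore pick up irrelevant variables and pass over prognostic ones.

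The rule is also incomplete. It does not say how a difference is judged, which variables are examined, what model is fitted, what effect measure results, or which analysis decides non-inferiority. All of these would be settled with the outcome data in hand. At stake is the credibility of a non-inferiority claim if the adjusted and unadjusted results fall on opposite sides of the margin.

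**Working it through.** **The plan's own figure.** Section 5 gives "we need 58 patients per group (chlorhexidine gluconate versus povidone iodine) to detect no difference with an alpha =0.05 and with 80% power". With equal true rates p in both arms and margin 0.10, n per arm = (z_alpha + z_0.80)² × 2p(1 − p) / 0.10². No UTI rate is stated, so 58 can only be back-solved:
- One-sided 0.05: (1.645 + 0.842)² = 6.18. At p = 0.0493, n = 618 × 0.0937 = 58.
- One-sided 0.025: n = 58 needs p of about 0.038.
- The one UTI rate in the document, in Section 2 ("33% of women develop UTIs in the 12 week period following surgical treatment for stress urinary incontinence"), gives 274 per arm (one-sided 0.05) or 348 (one-sided 0.025).

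The missing rate is a separate and more serious issue. It matters here because it leaves the UTI rate open, so I use 5%, 20% and 33%.

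**How often chance would trigger adjustment.** Assume that a difference means p < 0.05 and that k baseline variables are independent. The plan states neither. P(at least one) = 1 − 0.95^k: k = 5 gives 23%, k = 10 gives 40%, k = 15 gives 54%. Read literally, some difference will almost always exist.

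**Effect scale.** If the model were logistic, the odds ratio equivalent to a 10-point excess would be [(p + 0.10)/(0.90 − p)] / [p/(1 − p)]: 3.35 at p = 5%, 2.25 at 10%, 1.71 at 20% and 1.53 at 33%. With no control rate stated, no conversion is fixed.

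**Precision.** Simulation: 58 per arm, no true difference, five covariates of which one is prognostic, 4,000 trials per scenario. The covariate count, its strength and the p < 0.05 trigger are assumptions. Entries are the variance of the adjusted (standardised) risk difference divided by that of the unadjusted one.

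| UTI rate | Odds ratio per SD | Prespecified | Triggered |
|---|---|---|---|
| 5% | 1.5 / 2 / 3 | 1.017 / 1.005 / 0.958 | 1.013 / 1.012 / 0.997 |
| 20% | 1.5 / 2 / 3 | 0.982 / 0.945 / 0.861 | 1.008 / 0.991 / 0.981 |
| 33% | 1.5 / 2 / 3 | 0.972 / 0.912 / 0.800 | 1.008 / 0.985 / 0.953 |

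In seven of the nine settings prespecified adjustment saves at most 9% of variance. The exceptions are 14% and 20%, with a common outcome and a strong covariate. At a 5% rate the range is a 2% loss to a 4% gain. The triggered rule captures little of any gain. Power for non-inferiority (one-sided 0.05) changes by about −1 to +4 points with prespecified adjustment (largest: 0.380 to 0.424) and by less than 1 point with the trigger.

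A second simulation (6,000 trials per scenario, one prognostic binary covariate among ten, 25% prevalence, UTI risks of 3%/11%, 10%/35% and 25%/57% by covariate) gave 0.97, 0.92 and 0.92 prespecified, against 1.02, 0.99 and 1.01 triggered.

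**False non-inferiority at a true 10-point excess** (prognostic odds ratio 2 per SD, one-sided 0.05, control rates 5%, 20%, 33%):
- One fixed trigger at p < 0.05, risk difference kept, five covariates: 6.6%, 5.3%, 5.1%, against 6.8%, 5.4%, 5.4% unadjusted. No inflation.
- Claiming non-inferiority if the unadjusted result passes, or adjustment under a p < 0.05, 0.10 or 0.20 trigger does, ten covariates: 8.1%, 6.4%, 6.3%, against 6.7%, 5.5%, 5.2% unadjusted. Increases of 1.4, 0.9 and 1.1 points.

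Free choice of covariates or of effect scale was not simulated.

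**The case against.** The strongest defence is that the sentence describes an explanatory step. It follows the between-group tests and asks how far baseline differences account for what was seen. A reader might infer that the plan sets up two competing primary results; the text does not designate the adjusted analysis as a second primary. What stands is that the plan never says which result decides.

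A reader might also infer that the adjusted result cannot be compared with the margin. That would be true of a logistic odds ratio, but the plan says only that the analysis is multivariate. An identity-link model or a standardised risk difference could be set directly against 10 points. The supportable statement is that no effect scale is given, and the Wilcoxon-Mann-Whitney analysis has the same gap.

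Third, little numerical harm was shown. A fixed trigger did not inflate type I error, and the precision forgone is small at the roughly 5% rate at which 58 per arm reproduces. The fix below takes even that gain only in a supportive analysis. All of this stands, so precision is not the main argument.

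Finally, baseline differences are pure chance only among everyone randomised. Section 5 enrols up to 200 to obtain 116 with two-week follow-up, and Section 15 allows investigator withdrawal, so differences among those analysed need not be chance alone. That is a reason to adjust for prognostic variables chosen in advance, not for those that happen to differ.

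**Conclusion.** The concern holds for the rule itself: adjustment depends on observed imbalance, and the covariates, model, effect scale and deciding analysis are unspecified. No other section repairs this. Neither the adjusted nor the unadjusted analysis is tied, as written, to the margin.

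The size is modest. A free choice among results added about 1 percentage point of false non-inferiority under the assumptions above. The precision at stake is near nil at a 5% UTI rate and reaches 20% of variance only at a 33% rate with an odds ratio of 3 per SD. The trigger frequencies of 23%, 40% and 54% illustrate one reading of the text and are not properties of this plan. The documents do not support a stronger claim that the trigger by itself inflates type I error or costs substantial power. The case for change is that it removes a post-hoc choice at almost no cost.

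**What to change.** In Section 13:
- Delete the conditional sentence and do no significance tests of baseline variables; describe baseline characteristics by arm.
- State that the unadjusted difference in two-week UTI rates (chlorhexidine minus povidone iodine), with its confidence interval set against +10 percentage points, decides non-inferiority. Fix the interval level, since Section 5 does not say whether alpha 0.05 is one- or two-sided: one-sided 0.05 corresponds to a 90% interval, one-sided 0.025 to a 95% interval.
- Prespecify one supportive adjusted risk difference, either standardised from a regression model or Mantel-Haenszel, with two or three prognostic covariates named now and reported whatever the observed balance. Prior UTI history and type of procedure are candidates, but confirm that they are recorded: Section 12 lists only broad categories and the survey forms are not in the text reviewed.

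The cost is a few sentences, with no change to procedures, data collection or sample size. The downside is that the covariates are fixed before the data are seen and the list must be short: at a 5% UTI rate, 116 patients yield about 116 × 0.05 = 6 events.
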